Hypothesis 2. ENDS participants will exhibit better asthma control and improved pulmonary function on measures of spirometry (i.e., PEF, FEV1, FVC, FEV1/FVC ratio, FEF25-75) and self-reported respiratory symptoms (wheezing, bronchitis, shortness of breath, mucus production, and other symptoms).

[figure not shown]
Secondary Aims

Aim 2a. Examine the effects of ENDS provision on inflammatory and disease biomarkers, including (IL-6, TNF- α , CXCL9, MMP9, FENO) and tobacco toxicant exposure (cotinine, CO, NNAL) at weeks baseline and week 8.

Hypothesis 4. Levels of both inflammatory biomarkers and tobacco toxicant exposure will be improved among participants randomized to ENDS relative to assessment-only control.

Aim 2b. Examine the effect of ENDS provision on intention to quit smoking and smoking cessation self-efficacy.

Hypothesis 5. ENDS participants will have higher quit intentions, and smoking cessation self-efficacy than controls.

3. Materials, Methods and Analysis. *The study design, methods and procedures must be adequately described in order for the IRB to understand all activities in which human subjects will participate. The IRB must also be able to differentiate those procedures that are performed for research purposes from those that are performed for routine care or evaluation.*

Design Overview: This study will use a between-subjects (N=30) randomized (unequally allocated 2:1), controlled design to investigating the influence of complimentary ENDS provision on combustible cigarette and ENDS use (including substitution of smoking for ENDS use), cigarette dependence, pulmonary function, and clinical indicators and biomarkers over 16 weeks. Eligible participants will be randomized to one of two conditions: 1) receive ENDS and e-liquid for 8 weeks, including encouragement to fully switch from cigarettes to ENDS; or, 2) an assessment-only control condition wherein participants may continue their usual cigarette smoking behaviors. The study involves initial and in-person screening, a baseline session and 8 weekly visits, and a 16-week follow-up visit (i.e., 8 weeks after discontinuation of complimentary ENDS provision to the experimental group).

ENDS selection: We intended to use JUUL for the ENDS condition due to its market share and nicotine delivery comparable to combustible cigarettes. However, due to shifting perceptions of JUUL related to EVALI and because the products have similar nicotine delivery profiles, we chose the VUSE Alto.

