DOCUMENT: Statistical Design and Power

PROTOCOL TITLE: Complimentary Electronic Cigarettes for Harm Reduction among Adult Smokers with Asthma

NCT: NCT05278065

DOCUMENT DATE: 06/17/2020

Statistical Design and Power

Statistical Design

Initial data analysis will include descriptive analysis for the sample and within study condition, tests of attrition, missing data analysis, evaluation of distributional properties, and correlations among measures. Potential moderators of treatment outcome (e.g., compliance) will also be examined.

Quantitative Analyses

Aim 1 - Hypothesis 1: At Week 8, ENDS participants will smoke fewer cigarettes/day (CPD) and show reduced cigarette dependence relative to BL. Relative rates of CPD reduction and cessation across study arms will be examined. DVs: cigarettes per day (from TLFB); FTCD and WISDM scores. IVs: time; condition; time by condition interaction.

Aim 2 - Hypothesis 2: ENDS participants will exhibit better asthma control and self-reported respiratory symptoms (wheezing, bronchitis, shortness of breath, mucus production) versus baseline. Changes in lung function will be explored. Primary DVs: Asthma Control: ACT scores, Asthma Symptoms: ASUI scores, Mini-AQLQ scores; Secondary DVs: Spirometry: PEF, FEV₁, FVC, FEV₁/FVC ratio, and FEF₂₅₋₇₅. IVs: time; condition; time by condition interaction.

Aim 3 - Hypothesis 3: Biomarkers of exposure, toxicity, and inflammation will be lower in ENDS participants versus BL. DVs: Inflammatory and Disease Biomarkers: IL-6, FENO, Exposure and Toxicity: NNAL, TNE, TNE/NNAL ratio. IVs: time; condition; time by condition interaction.

Qualitative Analyses

Aim 4 - Hypothesis 4: High willingness to participate, high weekly retention, low attrition, and few reported barriers to engagement will demonstrate feasibility of complimentary ENDS provision for cigarette substitution. Hypothesis 5: Positive responses during qualitative exit interviews will demonstrate acceptability.

Analytic approach:

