Multiple approaches will be used to investigate smoking/ENDS use; respiratory function; and inflammatory and disease marker outcomes but will primarily focus on developing a longitudinal model based on intent-to-treat principles. Initially, t-tests (paired and independent samples) will quantify differences in outcomes across groups or time, and ANOVA will be used to investigate within, between, and within-between interactions. We will leverage the robustness of linear mixed effects models (LMEM) or generalized estimating equations (GEE) to examine outcomes within a longitudinal framework. Intraclass correlations (ICCs) of outcome variables within participant classes will be investigated. Model terms will include time, condition, and their interaction, and covary for potentially unbalanced baseline demographic and behavioral (e.g., smoking) factors across conditions. LMEM models will include random intercepts to account for subject-level differences in outcomes and investigate fixed linear, quadratic, and subject-level random effects of time. Appropriate LMEMs will be selected based on the distributional properties of the DV. We will investigate logarithmic transformations of the outcome where necessary. DVs with high resolution data (e.g., measure of cigarettes per day available weekly), will be modeled at the weekly level. All analyses will be conducted in R version 3.6.0, using the geepack package for GEE and lme4 package for LMEMs.

Missing data:

Systematic missing data due to attrition or other factors will be examined. We will first conduct Little's MCAR test on a dataset including all participant characteristics, covariates, primary, and secondary outcomes to evaluate whether missing data patterns are consistent with the Missing Completely at Random (MCAR) assumption. As data in longitudinal studies is rarely MCAR, we will initially use the VIM package in R to identify patterns of systematic missingness across time. We will also use t-tests and χ^2 tests to examine whether covariates and outcomes at week 8 vary as a factor of attrition at subsequent time points. Multiple-imputation will be used for sensitivity analyses of all primary and secondary outcome models following identification of predictors of missingness to help sustain the missing-at-random (MAR) assumption. Multiple imputation will be conducted in the *mice* package for R.

Power Analysis and Sample Size

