Tobacco use outcomes: Power and sample size calculations were conducted in GPower 3.1 based on between- and within-subjects analyses. [name] pilot trial examining 6 weeks of complimentary ENDS provision on tobacco use behaviors and nicotine dependence at weeks 6 and 10 (i.e., 4 weeks after final ENDS provision) found significant reductions between baseline and both time points in average cigarettes per day (baseline=19.6(8.2); week 6=6.7(7.9), $d=1.64$; week 10=8.8(8.3), $d=1.12$) and cigarette dependence (baseline=5.94(1.96); week 6=3.89(2.78), $d=.88$; week 10=3.50(3.08), $d=1.03$); all with large effects. However, given the unknown effect of providing free ENDS to adult smokers with asthma and the limited interpretability of effect sizes from pilot trials we chose to use a more conservative medium-large ($d=0.65$) effect size. With our planned enrollment ($N=30$), anticipated 10% dropout, and target power ($1-\beta=.8$), sample size was adequate to detect within-subject repeated measures (Aim 1) differences in the intervention (ENDS) group but was inadequate to detect between-subjects effects (i.e., group differences). Although power is below .80 to detect group differences, this pilot proposal will help determine the magnitude of these effects and inform the design of future research.

Respiratory outcomes: Investigations of respiratory symptoms and lung function change in 'healthy' smokers switching to ENDS have found very large ($h=1.94$) within-subjects effects for cough, very large ($h=1.50$) within-subjects effects for shortness of breath, and large ($d=.998$) within-subjects effects for FEF₂₅₋₇₅; also found were large ($d=.921$) between-subjects effects comparing successful to failed switchers. As these improvements may be even more pronounced for adults with asthma, the current planned enrollment achieves adequate power to examine these within-subjects (but not between-subjects) outcomes within the ENDS condition per the power and sample size analyses outlined above (Aim 3). However, analysis of spirometry are limited by the short follow-up period for the proposed pilot within-which changes in these metrics are not anticipated. As with the tobacco use outcomes, although power is below .80 to detect group differences, this pilot proposal will help determine the magnitude of these effects and inform the design of future research.

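### Adjustment covariates are tied to potential imbalance between arms, and the plan does not commit to adjusting each outcome for its own baseline value

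*SAP*

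**What the plan says.** The SAP (Analytic approach) puts a longitudinal model at the centre of the analysis: "Model terms will include time, condition, and their interaction". It adds that "LMEM models will include random intercepts to account for subject-level differences in outcomes". On covariates, the models will "covary for potentially unbalanced baseline demographic and behavioral (e.g., smoking) factors across conditions". There is no list of covariates, no definition or threshold for imbalance, and no statement that the baseline value of the outcome is always adjusted for.

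The hypotheses under Quantitative Analyses are framed against baseline, for example "ENDS participants will smoke fewer cigarettes/day (CPD) and show reduced cigarette dependence relative to BL", and time by condition is among the listed terms for Aims 1 to 3. This implies, without saying so, that baseline is a level of time. Before the models, "t-tests (paired and independent samples) will quantify differences in outcomes across groups or time"; no covariates are mentioned for these tests.

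**The concern.** In a randomised trial, baseline imbalance arises by chance. It does not show which variables predict the outcome. A criterion based on imbalance can admit factors that explain nothing and leave out the variable likely to explain most, the outcome's own baseline, when that happens to look balanced.

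What is at stake is precision. The SAP concedes that power for group differences is below .80 and justifies the comparison as a way to learn the size of the effect. With about 27 completers, an estimate noisier than the collected data allow weakens that product.

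**Working it through.** **Inputs.** The Protocol (Design Overview) gives a "between-subjects (N=30) randomized (unequally allocated 2:1), controlled design", hence 20 v 10. The SAP (Power Analysis and Sample Size) gives "anticipated 10% dropout", hence 18 v 9 if dropout is equal in the two arms, and d = 0.65. Alpha and the baseline-outcome correlation r are not stated. I assume two-sided 5% and r = .3, .5 and .7, with equal SDs at baseline and follow-up.

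**The plan's own figure.** Between-arm power by the noncentral t, with noncentrality d × √(n₁n₂/(n₁+n₂)):
- 18 v 9: 0.65 × √(162/27) = 0.65 × 2.449 = 1.592, df 25, power .334.
- 20 v 10: 0.65 × √(200/30) = 1.678, df 28, power .367.

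Both are below .80, so the SAP's statement reproduces.

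**Time-by-condition contrast.** With baseline as a level of time (time as categories, complete data), the Week 8 interaction equals the between-arm difference in mean change. In SD² units, the variance per participant is 2(1−r) for change and (1−r²) for baseline adjustment (ANCOVA). The ANCOVA variance is also multiplied by about 24/23 for estimating the slope. The noncentralities are 1.592/√(2(1−r)) and 1.592/√((1−r²) × 24/23). The power and root mean squared error (RMSE) columns come from simulation, 60,000 trials per setting; RMSE is from the runs with no true effect.

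| r | Noncentrality, change | Noncentrality, ANCOVA | Power, change | Power, ANCOVA | Loss | RMSE, change v ANCOVA |
|---|---|---|---|---|---|---|
| .3 | 1.592/1.183 = 1.345 | 1.592/0.974 = 1.634 | .250 | .349 | .099 | .479 v .395 |
| .5 | 1.592/1.000 = 1.592 | 1.592/0.885 = 1.800 | .335 | .409 | .074 | .407 v .360 |
| .7 | 1.592/0.775 = 2.055 | 1.592/0.730 = 2.182 | .508 | .559 | .051 | .316 v .298 |

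At r = .3 the change score also does worse than no adjustment (.250 v .334).

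**Effect of the covariate clause on that contrast.** A time-constant covariate entered as a main effect shifts all of a participant's values equally and cancels from change. In 30 complete simulated data sets (18 v 9, three time points, random intercepts), adding one moved the interaction estimate by less than 10⁻¹⁴ and its standard error by less than 10⁻⁵. The same cancellation applies if the added covariate is the baseline outcome itself.

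**Follow-up-only comparison.** Here the clause does matter. The SAP gives no trigger, so several were tried. With the baseline outcome as the only candidate:

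| r | No adjustment | Adjust if p<.05 / p<.10 / p<.20 | Adjust if difference >.25 / >.5 SD | Always ANCOVA |
|---|---|---|---|---|
| .3 | .334 | .330 / .329 / .328 | .335 / .329 | .349 |
| .5 | .332 | .329 / .328 / .332 | .361 / .335 | .409 |
| .7 | .337 | .338 / .341 / .355 | .432 / .360 | .559 |

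At p<.10 the loss against ANCOVA is .020, .081 and .218. The >.25 SD trigger loses less: .014, .048 and .127.

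With six non-prognostic candidates added (6,000 trials per setting, the same five triggers), the rule's power is .27-.31, .29-.32 and .31-.34. Fixed adjustment gives .34-.35, .41-.42 and .55-.57. Under p<.10, at correlations of .32, .52 and .64, the rule gives .30-.31 against .34, .42 and .50. Taken together, a rule triggered by a baseline test typically loses about 2-4 points at r = .3, 8-10 at r = .5 and over 20 at r = .7. The least favourable trigger at r = .5 loses up to .42 − .29 = .13.

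**The case against.** Four points on the other side have force.

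1. The largest losses belong to a comparison that is not the SAP's main model. That model already uses baseline through change, and imbalance-chosen main effects leave its interaction alone when data are complete. This stands. What remains there is the cost of a change score against baseline adjustment.

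2. A reader might infer that the imbalance criterion is no better than no adjustment at all. The calculations do not support this in general. With the baseline outcome as sole candidate at r = .7, RMSE is .305-.382 across the triggers against .408 unadjusted, and the >.25 SD trigger raises power from .337 to .432. Even with six noise candidates and p<.10, variance at r = .7 is 0.152 against 0.164. The statement is defensible only for power, under a significance-test trigger with several non-prognostic candidates, and the documents do not say that the candidates are non-prognostic. Smoking, the SAP's one example, is the baseline of the cigarettes/day outcome.

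3. A reader might also infer that covariates will be picked after seeing the arms differ. The wording may instead mean factors expected in advance to be vulnerable to imbalance at this sample size. The SAP describes no baseline test; it also names no covariate set.

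4. False positives are not inflated: at p<.10 with one candidate, type I error is .045, .041 and .032 at r = .3, .5 and .7. The effects that the SAP calls adequately powered are within the ENDS arm, where imbalance between arms is irrelevant.

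**Conclusion.** The point holds as one of efficiency and specification. Covariates are tied to potential imbalance, not prognostic value, and adjustment for each outcome's own baseline is not promised. In the main model as apparently intended, this gives up about 10, 7 and 5 points of between-arm power at r = .3, .5 and .7. In a follow-up-only or condition main-effect comparison, an imbalance-triggered rule loses little at r = .3 and a good deal at r = .5 and above.

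The sizes rest on 18 v 9 with equal dropout, d = 0.65, two-sided 5%, assumed correlations, equal SDs, a linear model and, for the main model, baseline entered as a time category with complete data. Near r = 0, baseline adjustment costs about one point of power (.322 v .334). Missing visits or covariates crossed with time would let the covariate clause reach the interaction as well. It is a cheap improvement, not a flaw that invalidates the analysis.

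**What to change.** Replace the covariate clause with a fixed rule. Each between-arm model takes post-baseline values as the outcome and includes the baseline value of the same outcome as a covariate. Outcomes other than cigarettes/day also include baseline cigarettes/day. Both apply whatever the observed balance. An equivalent choice is to keep baseline as a level of time and constrain the arm means to be equal there. Adding the baseline outcome as a covariate while leaving baseline as an unconstrained time level would not recover the loss.

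Tabulate baseline differences by arm for description only, and confine adjustment for other factors to a labelled sensitivity analysis.

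The cost is a short SAP amendment and one or two degrees of freedom. Other chance imbalances go unadjusted in the main model. Protocol Table 1 already schedules cigarette use, dependence, asthma, spirometry, IL-6, FENO and NNAL at baseline, so these need no new data.

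### The only missing-data sensitivity analysis stays within missing-at-random, so unrecorded return to baseline smoking after a participant's last visit is not explored

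*SAP*

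**What the plan says.** The SAP's Analytic approach section puts the main weight on a longitudinal intent-to-treat model, either a linear mixed effects model or GEE, with the choice left open. Simpler tests come first: "Initially, t-tests (paired and independent samples) will quantify differences in outcomes across groups or time", followed by ANOVA. Outcomes available weekly, such as CPD, are to be modelled weekly.

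The Missing data section begins with diagnostics. One is Little's test: "We will first conduct Little's MCAR test on a dataset including all participant characteristics, covariates, primary, and secondary outcomes". Missingness patterns are then described with the VIM package, and t-tests and chi-square tests ask whether "covariates and outcomes at week 8 vary as a factor of attrition at subsequent time points".

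The sensitivity analysis follows: "Multiple-imputation will be used for sensitivity analyses of all primary and secondary outcome models following identification of predictors of missingness", intended to "help sustain the missing-at-random (MAR) assumption" and run in the mice package.

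Neither document specifies an analysis that departs from MAR. There is no delta adjustment, return-to-baseline or reference-based imputation, pattern-mixture model or selection model. The SAP's Aim 1 also plans to compare cessation across arms, but no rule says how a participant with unknown smoking status is counted. The power section allows for "anticipated 10% dropout".

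**The concern.** A sensitivity analysis should vary the assumption on which the main result rests. A mixed model fitted by likelihood is valid under MAR, provided that the model is correct. Imputing under MAR and refitting holds that assumption fixed, so close agreement would be expected whether or not MAR is true. A reader of the trial report could nevertheless take the agreement as evidence of robustness.

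The scenario that matters is a participant in the ENDS arm who leaves and then returns to baseline smoking unseen. The trial is open-label, enrols smokers with no plan to quit, and measures CPD by self-report. Week 16 falls 8 weeks after free supply ends, with no visit in between (Protocol, Design Overview and Table 1). The estimated size of the effect is the pilot's declared product and is meant to inform later trials. An overestimate would carry forward into their design.

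**Working it through.** **Does any planned step examine departure from MAR?**

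| Planned step | What it can show | What it cannot show |
|---|---|---|
| Little's test | Evidence against MCAR | Whether data are MAR or not at random |
| VIM patterns | Which records are missing, and links to observed values | Unobserved values |
| Week 8 data compared by later attrition | Whether recorded smoking relates to loss before Week 16 | Dropout before Week 8; smoking after dropout |
| Multiple imputation against mixed model | Effect of adding predictors of missingness | Departure from MAR, since both assume it |
| Multiple imputation against unweighted GEE, t-tests or ANOVA | Effect of relaxing roughly MCAR to MAR | Departure from MAR |

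None of them does.

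**How far could the estimate move?** The plan gives no figure for the effect of missing data, so this is an illustration.

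Inputs:
- Allocation: N=30 at 2:1 (Protocol, Design Overview), so 30 × 2/3 = 20 in the ENDS arm.
- Dropout: 10% (SAP, Power Analysis and Sample Size), so 0.10 × 20 = 2 ENDS participants. The rates of 20% and 30% are assumptions.
- Pilot CPD (same section): 19.6 at baseline, 6.7 at week 6 and 8.8 at week 10, the last being 4 weeks after provision ended. The falls are 19.6 − 6.7 = 12.9 and 19.6 − 8.8 = 10.8.
- Assumption: those observed show the pilot's mean fall.

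Let p be the proportion missing and λ the share of the observed fall that is removed for dropouts. Then

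mean fall = observed fall × (1 − pλ).

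λ = 0 corresponds to MAR in this simple case, and λ = 1 to return to baseline.

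| p | 12.9, λ = 0.5 | 12.9, λ = 1 | 10.8, λ = 1 |
|---|---|---|---|
| 10% | 12.9 × 0.95 = 12.3 | 12.9 × 0.90 = 11.6 | 10.8 × 0.90 = 9.7 |
| 20% (assumed) | 12.9 × 0.90 = 11.6 | 12.9 × 0.80 = 10.3 | 10.8 × 0.80 = 8.6 |
| 30% (assumed) | 12.9 × 0.85 = 11.0 | 12.9 × 0.70 = 9.0 | 10.8 × 0.70 = 7.6 |

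For cessation, the rate among those observed is (quitters)/(observed). Counting missing as smoking gives (quitters)/(randomised), which multiplies the observed rate by 18/20 = 0.90 at the planned dropout.

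**Is there an added loss of power?** I used a two-sided paired t-test at the planning effect of 0.65, with alpha 0.05 assumed because the documents state none.
- Losing 2 of 20 (n = 18) gives power 0.74. Losing 4 of 20 (n = 16) gives 0.68.
- Keeping n = 20 with those participants' change set to zero, and the rest normal with mean 0.65 and SD 1, gives simulated power of 0.74 and 0.68.

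The values agree to two decimals because zero changes lower the variance as well as the mean. Return-to-baseline imputation therefore costs essentially no power beyond the dropout itself.

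**The case against.** Four points on the other side have force.

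1. *Most non-switching is on record.* Cigarette and ENDS use is collected by timeline follow-back at baseline, at each of Weeks 1 to 8 and at Week 16 (Protocol, Table 1). A participant who fails to switch and then leaves will usually have shown it already. Dropout explained by recorded smoking is MAR, and a correctly specified mixed model or imputation deals with it. This stands. A reader might infer that loss of non-switchers is in itself missing-not-at-random, but the documents do not support that. The gap is confined to smoking after the last record that the earlier history does not predict.

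2. *Imputation is not a mere repeat.* It relaxes the assumption if unweighted GEE is chosen, and for complete-case t-tests and ANOVA. Even beside a mixed model it may bring in predictors of missingness that the model lacks. This also stands, but imputation remains within MAR throughout.

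3. *Direction is not established.* No document gives reasons for dropout or rates by arm. It would be tempting to say that the error must favour ENDS. The documents support only that it could.

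4. *The numbers are small and this is a pilot.* At the planned rate about two ENDS participants are affected, and the illustrated fall is still 11.6 CPD. That limits the weight of the point. It does not remove it, since the pilot exists to estimate the size of effects.

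**Conclusion.** The point holds in a limited form. Every planned analysis of missing data stays within MAR, and agreement between a likelihood-based mixed model and MAR imputation would not test that assumption. The scenario left out is unrecorded return to baseline smoking after the last visit. It is most plausible at Week 16 and possible for anyone lost before Week 8. The missing rule for unknown cessation status is part of the same gap.

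The size is modest at the planned dropout: a 10% attenuation, from 12.9 to 11.6 CPD. It rises to 10.3 or 9.0 at assumed dropout of 20% or 30%. These figures assume that the pilot's fall applies to those observed and that every dropout is at baseline smoking. They do not bound the error, because a dropout could smoke more than at baseline. A reader might also expect the correction to reduce power further; the calculation does not bear that out. None of the figures shows a changed conclusion. This is an inexpensive improvement to the plan.

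**What to change.** In the SAP's Missing data section, for CPD and cessation at Weeks 8 and 16:

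- **(a) Simple bound.** Set missing CPD to the participant's own baseline value and count missing cessation status as smoking, in both arms.
- **(b) Delta-adjusted imputation.** In mice, remove between 0% and 100% of the observed reduction for ENDS dropouts. Report the delta at which the conclusion changes or, since between-group power is acknowledged to be low, how far the estimate moves across the range.
- **(c) Labelling.** Describe the MAR imputation as a supportive analysis, and state which main analysis it is compared with (mixed model or GEE), because that determines what agreement means.

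The cost is a short SAP addition and a few lines of R in a package already named. No new data or participants are needed. The downside is a little extra analysis and a less favourable bound reported beside the main result.

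### The claim of adequate within-subjects power for respiratory outcomes is not supported for the planned primary measures (ACT, ASUI, Mini-AQLQ)

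*SAP*

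**What the plan says.** The SAP (Power Analysis and Sample Size, Respiratory outcomes) and the protocol (Part III, section 4, Sample Size Considerations) carry the same paragraph. It cites within-subjects effects in healthy smokers switching to ENDS: h=1.94 for cough, h=1.50 for shortness of breath and d=.998 for FEF25-75. It adds large (d=.921) "between-subjects effects comparing successful to failed switchers", suggests that improvement may be greater in asthma, and concludes that "the current planned enrollment achieves adequate power to examine these within-subjects (but not between-subjects) outcomes within the ENDS condition". It refers for this to the power analyses above it and labels the outcomes Aim 3. The next sentence says that spirometry is not expected to change within the follow-up.

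The analyses above are those for tobacco use, where "we chose to use a more conservative medium-large ($d=0.65$) effect size", with N=30, "anticipated 10% dropout" and target power .8. The protocol's Design Overview describes a "randomized (unequally allocated 2:1), controlled design".

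The outcomes planned under SAP Aim 2, Hypothesis 2 are different: "Primary DVs: Asthma Control: ACT scores, Asthma Symptoms: ASUI scores, Mini-AQLQ scores". Spirometry, including FEF25-75, is secondary. The SAP's analytic approach centres on a longitudinal model following intention-to-treat principles.

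**The concern.** The paragraph asserts a property of the design, but its inputs do not reach the outcomes that Hypothesis 2 tests. Two of the three cited effects are differences in proportions, whereas the planned measures are scale scores. The third is for a measure that the authors do not expect to move. The cited samples are described as switching, while this trial recruits smokers with no intention to quit in the next 30 days and analyses everyone given ENDS.

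The documents disclaim between-group power but affirm within-group power. A flat result on ACT, ASUI or Mini-AQLQ could then be read as evidence against benefit from an adequately powered comparison, although no power for those scores was established.

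**Working it through.** **1. Cited effects against planned measures**

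| Cited effect | Place in SAP Hypothesis 2 |
|---|---|
| Cough, h=1.94 | Not among the named symptoms; not a listed measure |
| Shortness of breath, h=1.50 | Named as a symptom; not a listed measure in its own right |
| FEF25-75, d=.998 | Secondary measure; no change anticipated |
| None | ACT, ASUI, Mini-AQLQ (primary) |

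**2. Inputs**
- N=30 (SAP) and 2:1 allocation (protocol). The text does not say which arm is larger. Assuming it is ENDS, n = 30 × 2/3 = 20.
- Dropout 10% (SAP): 20 × 0.9 = 18 completers.
- d=0.65 and target power 0.80 (SAP).
- Alpha, sidedness, number of measurements and correlation are not stated. I assume a two-sided 5% paired t-test of baseline against week 8, with d standardised by the SD of the change. Paired t-tests are among the initial analyses that the SAP names.

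**3. The plan's own figure.** No numeric power is given for respiratory outcomes, only that it is adequate, so there is nothing to reproduce exactly. The d=0.65 analysis can be tested against the 0.80 target.

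Paired t power = P(|T| > t crit), where T is noncentral t with n−1 degrees of freedom and noncentrality d√n.
- n=18: noncentrality 0.65 × √18 = 2.758, t crit = 2.110 on 17 df, power **0.74**.
- n=20 (no dropout): noncentrality 0.65 × √20 = 2.907, t crit = 2.093 on 19 df, power **0.79**.
- Smallest n reaching 0.80: 21 completers. Allowing for dropout, 21/0.9 = 23.3, so 24 enrolled in the ENDS arm.
- Smallest d with power 0.80: 0.70 for n=18, 0.66 for n=20.

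**4. Other settings, n=18, d=0.65**
- One-sided 5%: power 0.84 (detectable d 0.61).
- Repeated-measures ANOVA with f = d/2 = 0.325, correlation ρ, m measurements and noncentrality f²nm/(1−ρ):
  - m=2, ρ=0.5: 0.1056 × 18 × 2/0.5 = 7.6, power 0.74.
  - m=3, ρ=0.5: 0.1056 × 18 × 3/0.5 = 11.4, power 0.83.

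Whether 0.80 is met therefore turns on settings that neither document reports.

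**5. The cited FEF25-75 effect.** Taken at face value, d=.998 with n=18 has power 0.98. As an illustration of dilution, suppose that it applies to a share s of the arm who switch and that the rest do not change. The arm-level effect is 0.998s, or 0.998s/√(1 + s(1−s)0.998²) if the mixture also widens the SD.

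| s | Power, SD unchanged | Power, mixture SD |
|---|---|---|
| 80% | 0.89 | 0.84 |
| 70% | 0.80 | 0.72 |
| 60% | 0.67 | 0.58 |
| 50% | 0.51 | 0.43 |

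Under this model 0.80 needs about 70% switching (SD unchanged) or 76% (mixture SD). The documents give no value for s. Zero change in the remainder is also an assumption, since partial substitution might help.

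**The case against.** The strongest reply is that the claim does not rest on the large cited effects alone. It refers to an analysis that deliberately used a smaller effect, 0.65, because the effect in smokers with asthma was unknown. That figure is about what .998 becomes if 65% switch (0.998 × 0.65 = 0.649). The power section speaks of within-subject repeated measures. ACT and ASUI are scheduled three times and Mini-AQLQ weekly as well, so a calculation exceeding 0.80 is quite possible. The study is called a pilot, its between-group power is openly conceded, and shortness of breath does appear in Hypothesis 2.

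Much of this stands. It rules out two stronger readings that a reader might infer:
- *The ENDS arm lacks adequate power.* This is not shown. Without a switching rate or an effect for the primary scores, adequacy can be neither confirmed nor refuted, and some plausible settings exceed 0.80.
- *The cited within-subjects effects come only from people who successfully switched.* The text says smokers switching to ENDS and does not define that sample. Only the d=.921 contrast separates success from failure.

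The reply does not fill the gap. The 0.65 was chosen for tobacco use and is not justified for any asthma score. It falls short of 0.80 on a two-sided paired t-test, and the settings that would rescue it are not reported.

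**Conclusion.** The concern holds as a gap in support: adequate within-subjects power is asserted for respiratory outcomes but not demonstrated for the primary ones. At the plan's d=0.65, power is 0.74 with 18 completers and 0.79 with 20, two-sided; the 18-completer case can detect about 0.70. These figures assume that ENDS is the larger arm, dropout is 10% in that arm, alpha is 5%, there are two time points, and d is standardised by the SD of the change. The 0.70 threshold belongs to that test only. The switching figures show sensitivity and are not estimates.

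A separate labelling error is plain: Aim 3 in the SAP is the biomarker aim, and respiratory outcomes are Aim 2. The protocol lists them under Aim 1b and has no Aim 3 for this trial.

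**What to change.** In both documents, replace the respiratory power sentence with: *With 18 ENDS completers, a two-sided 5% paired t-test has 80% power for a standardised within-arm change of about 0.70 (power 0.74 at d=0.65). No effect size is available for ACT, ASUI or Mini-AQLQ under intention to treat, so no power is claimed for them, and Hypothesis 2 is reported as estimates with 95% confidence intervals.*

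If a different test was run in GPower, state its alpha, sidedness, number of measurements and correlation, with the matching figure. State which arm is the larger. Change the label to Aim 2 in the SAP and bring the protocol's label into line with its own numbering.

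The cost is wording, and a stated property becomes less favourable. Enrolment and procedures do not change.
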